The clinical trial was carried out at the Orthodontic Clinic of UNIBE's Postgraduate Unit, Santo Domingo, Dominican Republic, from June 2017 to November 2018. The established inclusion criteria were patients with 18-40 years old, systemically healthy, without active dental caries lesions or periodontal diseases, who were candidates for fixed orthodontic appliances. Smokers and pregnant patients were excluded. Participants were discarded if they decided voluntarily to abandon the study of the orthodontic treatment or if they didn't attend to the periodical check-ups.

Randomization

A simple randomization procedure was executed by the principal investigator to allocate the participants into one of the study groups. A computer-generated list of numbers was created using the software SPSS V21.0, with a 1:1.25 allocation ratio. The aforementioned researcher didn't participate in the data recollection process.

Two dentists were in charge of the study logistic. They enrolled and allocated the participants according to the order of arrival and following the list of random numbers. A coding system was used as a concealment mechanism, which consisted of colored labels attached to the participants' file. This system was only known by the logistics managers and the interviewer (the periodontist who provided OHI and MI). Thus, the participant and the evaluator (the periodontist who recorded the data) were masked.

Study intervention

The patients were invited to participate in the research in their first appointment with the orthodontic postgraduate dentist. Then, on the second appointment, the fixed orthodontic appliance was placed and the intervention began. A questionnaire to collect sociodemographic information was administered by the interviewer.

The interviewer was also in charge of providing oral hygiene instructions for both groups. All the participants received a G.U.M. kit with special orthodontic hygiene tools. Then, the patients of the experimental group received a motivational interviewing session. It is important to point out that the periodontist was trained and evaluated by two expert psychologists in MI, who also supervised the interviewer to ensure that the intervention was properly applied. Additionally, all the staff related to the research was also trained.

Afterwards, the clinical parameters were measured by another periodontist. The primary endpoint with respect of the efficacy of MI was the Simplified Oral Hygiene Index (SOHI). Additional parameters were recorded, such as the Gingival Index (GI), Periodontal Probing Depth (PPD) and Bleeding on Probing (BoP), with the purpose of evaluating the periodontal stability.

Monthly follow-up appointments were scheduled for the orthodontic check-ups to deliver a new G.U.M. kit, to reinforce the OHI and MI and to register the periodontal parameters. The important data for this research was the one recorded at baseline, three and six months after the intervention.

Statistical analysis

Mean SOHI, GI, PPD and BoP scores were compared between groups across three time points using repeated-measures mixed-model analysis of variance. Tests for equality of variances and sphericity to check for homoscedasticity were performed due to the problem of sample attrition. Nevertheless, it was not found any violation to these assumptions in any of the variables included

in the analysis. SPSS software was used for all calculations (IBM SPSS 25th version). Due to the nominal level of measurement of the variable BoP, it was performed a chi-squared test for each three time points to check if there were any differences between the two experimental conditions.

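### Colour labels on files cannot conceal the next assignment from the dentists who both enrol and allocate, and they do not support the claim that participants were masked

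*Combined protocol and SAP*

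**What the plan says.** The Randomization section gives these steps:

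- **Sequence.** "A simple randomization procedure was executed by the principal investigator to allocate the participants into one of the study groups". The list was computer-generated with a 1:1.25 ratio, and this investigator took no part in collecting data.
- **Entry and assignment.** Two dentists ran the logistics. "They enrolled and allocated the participants according to the order of arrival and following the list of random numbers".
- **Concealment.** "A coding system was used as a concealment mechanism, which consisted of colored labels attached to the" participants' files. "This system was only known by the logistics managers and the interviewer", the interviewer being the periodontist who gave the hygiene instructions and the MI.
- **Masking.** "Thus, the participant and the evaluator (the periodontist who recorded the data) were masked".

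Under Study intervention, "The patients were invited to participate in the research in their first appointment with the orthodontic postgraduate dentist". The appliance was fitted and the intervention began at the second appointment. Both arms met the interviewer, received hygiene instructions and were given a kit. Only the experimental arm then had an MI session. A different periodontist took the clinical measurements afterwards, and the monthly visits were used to reinforce both the instructions and MI.

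Under Sample and eligibility criteria, patients had to be "without active dental caries lesions or periodontal diseases", among other conditions. The same section lists recruitment, consent and randomisation in that order for the 45 participants. The trial ran "from June 2017 to November 2018".

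**The concern.** Allocation concealment means that whoever decides on a patient's entry cannot know which arm comes next. The plan puts entry and assignment in the same two pairs of hands, has those hands follow the list, and names as concealment a code that they can read. If an enrolling dentist could see the next assignment, decisions on eligibility or on whether to enter a patient could differ by arm, and the arms would no longer be comparable by design.

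The masking sentence raises a second problem. It treats the labels as sufficient to mask participants, yet participants can tell whether they had an interview. Readers who judge the trial by its safeguards will credit it with concealment and participant masking that the described procedure does not provide.

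**Working it through.** The plan attaches no figure to this point. The check is mainly a matter of setting the roles side by side, followed by two short calculations.

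**1. Who knows what.** This reads the logistics managers as the two dentists in charge of logistics, which is the natural reading.

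| Role | Task | Follows the list | Knows the colour code |
|---|---|---|---|
| Principal investigator | Generates the list | Creates it | Not among those named |
| Two logistics dentists | Enrol and allocate | Yes | Yes |
| Interviewer | Instructions and MI | Not stated | Yes |
| Evaluator | Clinical measurements | Not stated | No |

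A label goes on the file of a person who is already a participant, so it encodes an assignment already made. Among the roles above it can hide the arm from the evaluator, which is masking. It cannot hide a future assignment from the two dentists. The sequence being generated by someone else does not change this, because the dentists work from that sequence. The text describes no envelopes, central release or third-party hold on the list.

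**2. What the list is worth to an enroller.** With simple randomisation at 1:1.25, earlier assignments say nothing about later ones. Without the list, the best guess is always the larger arm, and it is right with probability 1.25/(1 + 1.25) = 1.25/2.25 = 0.556. With the list and the code in view, the assignment is known with probability 1. The protection that simple randomisation gives therefore depends on the list being out of sight.

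**3. Participant masking.** The stated ground is the label. The difference the participant experiences is an MI session, reinforced monthly, in one arm only. No sham session or attention control is described. A file label cannot hide that difference, so the inference fails. Because both arms met the same interviewer and received instructions and a kit, the most that could hold is that participants did not know which arm was the experimental one.

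**4. Effect on the analysis.** The sample size is built on the group-by-time interaction for the Simplified Oral Hygiene Index. Take the arm difference at baseline, 3 and 6 months and subtract its mean over visits:

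- Constant difference d: (d, d, d) − d = (0, 0, 0). The interaction is untouched.
- Difference growing from 0 to d: (0, d/2, d) − d/2 = (−d/2, 0, +d/2). The interaction is affected unless d = 0.

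Selection on baseline level alone would thus cancel in the powered test, but selection on how hygiene is likely to change would not. The cancellation applies only to the interaction. Bleeding on probing is also tested by chi-squared at each visit, where a constant difference does not cancel. The documents give no value for d.

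**The case against.** The strongest reply is that the text leaves a step unreported and does not show a failure. Following the list is compatible with the principal investigator releasing one assignment at a time. Order of arrival limits re-ordering, consent is listed before randomisation, and age, smoking and pregnancy leave little to judge. The plan does not say who assessed caries and periodontal status, so it is not shown that the logistics dentists exercised that judgement. On masking, the claim may have meant only that participants did not know the hypothesis, and the consent wording is not available to check. Since the trial is finished, redesign cannot help it.

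Much of this stands, and it limits the conclusion. No bias is shown, the risk turns on whether the list was visible before entry was final, and the eligibility assessor is unknown. It does not rescue the two statements the plan makes. The plan names the labels as the concealment mechanism, and they are not one whoever held the list. It derives participant masking from the labels, and that does not follow whatever participants were told. Order of arrival and prior consent constrain the dentists but do not show that assignments were withheld while eligibility was being decided, and the caries and periodontal criterion still calls for clinical judgement.

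**Conclusion.** The concern holds. As described, the labels do not conceal the next assignment from the dentists who enrol, and they do not support participant masking. Evaluator masking is supported: the code was restricted to others and a separate periodontist recorded the data. Visible labels on files leave only a small residual risk there.

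Confidence is high about what the text describes and does not extend to any bias having occurred. The size of a bias cannot be estimated from the documents. It would be zero in the powered interaction for a constant arm difference, and of unknown size for one that changes over the visits. This should be corrected, because the plan claims safeguards that its own description does not deliver.

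**What to change.** **Completed trial.** First state who held the list and when each assignment was released. If assignments were withheld from the enrolling dentists until entry was final, describe how. If they were not, or if this cannot be established, report that allocation concealment was not demonstrated. In either case, stop describing the labels as concealment, and restrict the masking claim to the evaluator unless there is separate support for participant masking. The cost is wording only, possibly with a less favourable statement of trial quality.

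**A repeat of the design.** The principal investigator keeps the list. Assignments go into sequentially numbered sealed opaque envelopes, or an equivalent one-at-a-time release. The interviewer, who already knows the arm under the present plan, opens each one only after eligibility and consent are final, and preferably after the baseline measurement. Labels stay off files that the evaluator handles. This means preparing envelopes and changing the hand-off among existing staff, with no new personnel. The preferred version also reorders the second appointment, because the clinical measurement now follows the intervention session.
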